12.2 Sample Size/Accrual Rate

We anticipate approximately 150 patients to be screened for inclusion into our study, however, 15 will likely be screening failures or dropouts. Therefore, we propose a sample size of N=135. We anticipate to accrue approximately 30-50 subjects/year over the course of our 4-year study duration.

12.3 Stratification Factors

Not applicable.

12.4 Analysis of Endpoints

12.4.1 Analysis of Primary Endpoints

1. Clinical response at week 8 post-FMT, as defined by the reduction of the Mayo scoring system by >3 points (+30% reduction) with an accompanying decrease in the sub-score for rectal bleeding of at least 1 point (Section 10.1.2.2).

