efficacy of two-donor fecal microbiota preparation (FMP) delivery by colonoscopy. The primary outcome was clinical response at week 4 with secondary endpoints including clinical remission, mucosal healing at week 4 and safety profile. Overall, 34 patients were screened, and 20 patients were enrolled. Seven patients (35%) achieved a clinical response (Mayo score ≥ 3 and a bleeding subscore ≤ 1) by week 4. Three patients (15%) were in clinical remission at week 4 (Mayo score ≤ 2 and no subscore > 1), and two of these patients (10%) achieved mucosal healing (endoscopy subscore of 0). Paired analysis showed a significant improvement in Mayo score (Median decrease of 1.5, $p = 0.03$) and endoscopic subscore (Median decrease of 0.5, $p = 0.002$).

Further microbiome analysis revealed that signatures of donor-derived microbiota correlate with clinical response¹⁸. Taxonomic analysis revealed enrichment of *Ruminococcus*, *Odoribacter*, and *Christensenellaceae* in healthy donors and responders, but absent in patients with active disease. In contrast, patients who did not respond to treatment had failed to eradicate *Fusobacteria*, *Finegoldia* and *Collinsella*. To determine the fecal microbial composition and function at species/strain level, we performed metagenomic sequencing of a complete set of three samples (donor, recipient pre, recipient post) from three responder patients, who had met the primary endpoint of our pilot FMT trial. Relative abundances of microbial species were determined by Metaphlan2 and protein encoding genes profiling were determined by HUMAnN2 pipeline. Analysis of the previously identified transferrable genus of *Ruminococcus* revealed, that of the several species and strains present in the patient samples, abundance of only *Ruminococcus* torques was significantly enriched in responders. Collectively, this data revealed that response to single *colonoscopic* delivery correlated with engraftment of key species of transferrable bacteria in the responder patients. Further studies are required to determine factors that enhance the engraftment of these bacteria and increase the efficacy of this therapy.

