4.2 Inclusion Criteria

1. Male or Female \geq 18 years of age.
2. Documentation of prior history of mild to moderate UC.
3. Endoscopy confirmed active UC \geq 15 centimeters at day 0 screening colonoscopy.

- a. As defined by a total Mayo scoring of 4-10 with an endoscopic sub-score ≥ 1 and a stool frequency or rectal bleeding sub-score of ≥ 1 .
4. Patients must have a descending intact colon.
5. Patients taking steroid or biologic therapy must be on a stable dose for 4 weeks prior to screening and maintained throughout the trial.
6. Eligible patients willing to undergo serological and fecal screening testing prior to FMT to document baseline status:
 - a. Urine Testing
 - i. Pregnancy test (women with childbearing potential)
 - b. Blood Testing
 - i. B-HCG (research purposes)
 - ii. CBC, ESR, CRP, and BMP (standard of care)
 - iii. HIV, type I and II (standard of care)
 - iv. Hepatitis A B C Profile (standard of care)
 - v. RPR (*treponema pallidum*) (research purposes)
 - vi. CMV IgM (standard of care)
 - vii. Quantiferon-TB (standard of care)
 - c. Stool Testing
 - i. Calprotectin (standard of care)
 - ii. Clostridium Difficile Toxin PCR (standard of care)
 - iii. Ova & parasites (standard of care)
 - iv. Gastrointestinal Pathogen PCR Panel (standard of care)
 1. *Campylobacter* species
 2. *Plesiomonas Shigelloides*
 3. *Salmonella* Species
 4. *Vibrio* Species
 5. *Vibrio cholerae*
 6. *Yersinia Enterocolitica*
 7. Enterotoaggregative *E. coli* (EAEC)
 8. Enteropathogenic *E. coli* (EPEC)
 9. Enterotoxigenic *E. coli* (LT/ST)
 10. Shigalike toxin producing *E.coli* I (STX/ST2)
 11. *Cryptosporidium*
 12. *Cyclospora cayetanensis*
 13. *Entamoeba cayetanensis*
 14. *Giardia*
 15. *Adenovirus* F 40/41
 16. *Astrovirus*
 17. *Norovirus* GI/GII
 18. *Rotavirus* A
 19. *Sapovirus*
 20. *GID* PCR INTERP

7. Patients must discontinue anti-rCDI antibiotics (e.g. vancomycin, fidaxomicin) 48 hours prior to FMT delivery procedure.

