10.1 Response Criteria

10.1.1 Primary Endpoint Assessments

10.1.1.1 Mayo Scoring System³⁰

The Mayo Scoring System will be used for the assessment of ulcerative colitis activity. It is a composite score that ranges from 0-12 based on the following four categories: bleeding, stool frequency, physician assessment, and endoscopic findings. A partial Mayo Score ranges from 0-9 and can also be utilized if no endoscopic visualization is available to assess disease activity.

Study subjects will be evaluated by a full Mayo score at day 0 and week 8, and a partial Mayo score at the week 4 clinic visit. Both clinical response and remission will be evaluated at week 8 post-FMT. Clinical response is described as a reduction of the Mayo score by >3 points and >30% reduction from baseline with an accompanying decrease in the sub-score for rectal bleeding of at least 1 point. Clinical remission will be defined by Mayo score \leq 2 without any sub-score >1, and Mayo endoscopic sub-score 0-1.

Table 2. Mayo Scoring System for the assessment of ulcerative colitis activity.

Stool frequency [†]
0 = Normal no. of stools for this patient
1 = 1 to 2 stools more than normal
2 = 3 to 4 stools more than normal
3 = 5 or more stools more than normal
Subscore, 0 to 3
Rectal bleeding [‡]
0 = No blood seen
1 = Streaks of blood with stool less than half the time
2 = Obvious blood with stool most of the time
3 = Blood alone passes
Subscore, 0 to 3
Findings on endoscopy
0 = Normal or inactive disease
1 = Mild disease (erythema, decreased vascular pattern, mild friability)
2 = Moderate disease (marked erythema, lack of vascular pattern, friability, erosions)
3 = Severe disease (spontaneous bleeding, ulceration)
Subscore, 0 to 3
Physician's global assessment [§]
0 = Normal
1 = Mild disease
2 = Moderate disease
3 = Severe disease
Subscore, 0 to 3

* The Mayo score ranges from 0 to 12, with higher scores indicating more severe disease. Data are from Schroeder et al.²⁴

† Each patient serves as his or her own control to establish the degree of abnormality of the stool frequency.

‡ The daily bleeding score represents the most severe bleeding of the day.

§ The physician's global assessment acknowledges the three other criteria, the patient's daily recollection of abdominal discomfort and general sense of well-being, and other observations, such as physical findings and the patient's performance status.

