12.1 Sample Size and Analysis Plan

Prior studies and clinical experience involving FMT suggests a 27% response rate from a null rate of diet alone at 7%. Based on previous work¹⁸, we estimate the effect size of clinical response to FMT+fiber in patients with IBD to be approximately double the FMT-alone group (i.e., 55% vs. 27%, respectively). Recruitment of ~135 subjects with 45 patients per arm was calculated assuming a 55% response rate at 8 weeks in the FMT+fiber arm and a 27% response rate at 8 weeks in the FMT-alone arm, with approximately 80% power to detect this difference (using a two-sided significance level of 0.05)³¹. We will conduct pairwise chi-square analysis between the study arms of interests to directly address the primary study objective to detect a difference in clinical response (i.e. FMT+ fiber versus FMT alone). The remaining two pairwise comparisons can be considered as secondary aims and thus no multiple comparison adjustment is needed.

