12.4.2 Analysis of Secondary Endpoints

- a. Clinical remission at week 8 post-FMT, as defined by Mayo score ≤ 2 without any sub-score >1
- b. Endoscopic response or remission, as defined as a Mayo endoscopic sub-score 0-1 with at least a 1-point reduction from baseline or a Mayo endoscopic sub-score of 0
- c. Safety will be assessed by:
 1. Subject mucosal biopsies, stool and blood testing.
 2. Subject symptomatology via medical interview, physical exam, and Mayo score and change in standard UC medications.
 3. Number and type of treatment related adverse events
 4. Number and type of disease-related complications such as hospitalizations, surgeries and endoscopies, medical complications, and mortality.

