12.6.2 Evaluation of Response

All subjects included in the study will be assessed for response to treatment if they meet all inclusion and exclusion criteria, and then receive either placebo or investigational FMP250 treatment during the screening colonoscopy.

13. Adverse Event Reporting Requirements

Adverse event (AE) monitoring and reporting is a routine part of every clinical trial. The investigator will be required to provide appropriate information concerning any findings that suggest significant hazards, contraindications, side effects, or precautions pertinent to the safe use of the drug or device under investigation. Safety will be monitored by evaluation of adverse events reported by subjects or observed by investigators or research staff, as well as by other investigations such as clinical laboratory tests, x-rays, electrocardiographs, etc.

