13.2.4 Protocol-Specific Exceptions to SAE Reporting

A suspected clinical endpoint event, regardless of when the event occurs, is not to be reported as an AE or SAE or reported in an expedited manner as an SAE. The suspected clinical endpoint event includes:

- Recurrent UC flare
- Initial response to therapy with initial reduction to Mayo score ≤ 3 with an accompanying decrease in the sub-score for rectal bleeding of at least 1 point or an absolute sub-score for rectal bleeding of 0 or 1

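### Patients may enter with a rectal bleeding sub-score of 0, but primary response requires that sub-score to fall by at least 1 point, so they can never be responders

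*Combined protocol and SAP*

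**What the plan says.** **Entry.** Section 4.2, criterion 3a, requires a total Mayo score of 4 to 10, an endoscopic sub-score of at least 1, and "a stool frequency or rectal bleeding sub-score of" at least 1. Either symptom is enough. Nothing in Section 4.3 excludes a patient without bleeding.

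**Primary endpoint.** Section 10.1.1.1 requires a Mayo fall of more than 3 points and more than 30% from baseline, "with an accompanying decrease in the sub-score for rectal bleeding of at least 1 point". Section 12.4.1 repeats the bleeding condition: "with an accompanying decrease in the sub-score for rectal bleeding of at least 1 point (Section 10.1.2.2"). Neither section offers an alternative. Table 2 scores bleeding from 0 to 3, with 0 meaning no blood.

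**Who is assessed.** Section 12.6.2: "All subjects included in the study will be assessed for response to treatment if they meet all inclusion and exclusion criteria" and receive active or placebo FMP250 at the day 0 colonoscopy.

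**Related definitions.**
- Section 12.4.2: "Clinical remission at week 8 post-FMT, as defined by Mayo score" of 2 or less with no sub-score above 1. There is no bleeding-change condition.
- Section 13.2.4, on exceptions to SAE reporting, describes an initial response by the same bleeding fall "or an absolute sub-score for rectal bleeding of 0 or 1".
- Section 2.2 reports the pilot: "Seven patients (35%) achieved a clinical response", where the bleeding condition was an absolute sub-score of 1 or less.

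**Sample size.** Section 12.1 plans 45 patients per arm for about 80% power at two-sided 0.05, "assuming a 55% response rate at 8 weeks in the FMT+fiber arm and a 27% response rate at 8 weeks in the FMT-alone arm".

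**The concern.** The entry rule and the endpoint do not fit together. A patient admitted on stool frequency, with bleeding 0, has no bleeding points to lose, so the result is fixed at randomisation whatever the treatment does. The missing-data sensitivity analyses in Section 12.1 do not address this, because the week 8 data are present. Covariate adjustment cannot make an impossible outcome possible.

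Three things are at stake:
- **Classification.** A patient can be in clinical remission under Section 12.4.2 and a primary failure under Section 12.4.1.
- **Interpretation.** The response rate in an arm cannot exceed 1 − q, where q is the share of that arm entering with bleeding 0.
- **Power.** It could be lower than planned if the 55% and 27% in Section 12.1 describe only patients who are able to respond.

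**Working it through.** **1. The plan's own power figure.** Inputs from Section 12.1: p1 = 0.55, p2 = 0.27, n = 45 per arm, two-sided alpha 0.05 (z = 1.96). The mean rate is 0.41.

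- Null standard error (pooled): √(2 × 0.41 × 0.59 / 45) = 0.1037
- Alternative standard error: √(0.55 × 0.45 / 45 + 0.27 × 0.73 / 45) = 0.0994
- Pooled power: Φ[(0.28 − 1.96 × 0.1037) / 0.0994] = Φ(0.77) = 78.0%
- Unpooled power: Φ[0.28 / 0.0994 − 1.96] = Φ(0.86) = 80.4%

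The stated figure of about 80% reproduces.

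**2. Can a bleeding-0 entrant respond?** Four sub-scores of 0 to 3 give 4⁴ = 256 profiles. Criterion 3a admits 166. Of these, 32 have bleeding 0:

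| Baseline Mayo | 4 | 5 | 6 | 7 | 8 | 9 | Total |
|---|---|---|---|---|---|---|---|
| Profiles with bleeding 0 | 6 | 8 | 8 | 6 | 3 | 1 | 32 |

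Each of the 32 was checked against all 256 possible week 8 profiles. The number able to meet the current definition is 0 of 32. It is still 0 if the Mayo condition is read as at least 3 points instead of more than 3.

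**3. Remission counted as failure.** Eleven profiles satisfy the remission definition. There are 1,430 moves from an eligible baseline into one of them in which no sub-score worsens, and 206 of these start at bleeding 0. All 206 are primary failures. Of these, 159 meet both total-score conditions and fail on bleeding alone; the other 47 also miss the more-than-3 condition. If at least 3 is meant, 194 fail on bleeding alone.

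**4. Effect on rates and power.** The documents do not give q, so the values below are assumptions. There are two readings of 55% and 27%.

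- *Reading A:* they are all-patient rates under the written rule. Planned power stands, but the rates among patients able to respond must be 0.55 / (1 − q) and 0.27 / (1 − q).
- *Reading B:* they apply only to patients able to respond, and both arms dilute in proportion. The observed rates are then 0.55(1 − q) and 0.27(1 − q).

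| Assumed q | A: rates needed among those able to respond | B: observed rates | B: pooled power, 45 per arm |
|---|---|---|---|
| 0% | 55% vs 27% | 55.0% vs 27.0% | 78.0% |
| 10% | 61% vs 30% | 49.5% vs 24.3% | 70.4% |
| 20% | 69% vs 34% | 44.0% vs 21.6% | 62.3% |
| 30% | 79% vs 39% | 38.5% vs 18.9% | 53.9% |

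Section 12.1 does not say which reading applies.

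**5. What a repair would change.** The counts are non-worsening baseline-to-week-8 pairs that qualify as response, with the Mayo fall read as more than 3.

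| Bleeding condition | Qualifying pairs | Added | Source of additions |
|---|---|---|---|
| Fall of at least 1 (current) | 3,297 | – | – |
| Fall of at least 1, or 0 at week 8 | 3,636 | 339 (+10%) | all from baseline bleeding 0 |
| Fall of at least 1, or 0 or 1 at week 8 | 3,990 | 693 (+21%) | 339 from bleeding 0, 354 from bleeding 1 |

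Under the second row, all 32 bleeding-0 profiles can respond. If at least 3 is meant, the count goes from 3,979 to 4,495 (516 added, +13%), again all from bleeding 0.

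**The case against.** The logical conflict is hard to dispute; its weight can be disputed.

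- **The affected share is unknown.** This stands. The 32 of 166 are score combinations, and 28 of the 32 have totals of 4 to 7, so a fall from 9 to 0 is the extreme case.
- **The power loss is conditional.** This stands. Section 12.1 gives arm-level rates, and taken as all-patient rates they leave the planned power intact. The pilot does not settle the matter: it was open-label, no fiber arm is described, and its response rate was 35%, not 27%. It shows only that the study cited for the doubling used a bleeding condition that a bleeding-0 patient could meet.
- **Requiring bleeding to improve is a legitimate, stricter endpoint.** It is the same in all arms, and the secondary endpoints still record benefit in these patients. This is true, and it explains why type I error is untouched. But a stricter endpoint should be attainable by everyone assessed on it, and here it is not.
- **The repair does not remove every remission that counts as failure.** Correct. Of 442 such non-worsening moves, it rescues 159 and leaves 283: the 47 from bleeding 0 that miss the Mayo fall, and 236 from bleeding 1 to 3. Of those 236, 117 miss the Mayo fall and 119 meet it without a bleeding fall. Those patients could have responded, so they are outside this defect.
- **Changing a primary endpoint is a serious step.** Enrollment is listed as 2019–2023, and the documents do not show whether amendment before unblinding is still possible. That limits when the repair can be made, but does not remove the reason for it.

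**Conclusion.** The concern holds. As written, any patient entering with bleeding 0 is a certain primary non-responder. This follows from Sections 4.2, 10.1.1.1, 12.4.1 and 12.6.2 alone and needs no assumption about patient mix. It is the same under either reading of the Mayo fall.

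The certain harm is misclassification: the primary endpoint cannot record benefit in these patients, and each arm's rate is capped at 1 − q. There is no type I error problem. The size in patients depends on q, which the documents do not give. A fall in pooled power to about 70%, 62% or 54% at an assumed q of 10%, 20% or 30% follows only if 55% and 27% refer to patients able to respond and both arms dilute in proportion. Otherwise the stated power stands. This should be fixed, but it does not invalidate the randomised comparison.

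**What to change.** 1. By amendment before unblinding, change the bleeding condition in Sections 10.1.1.1 and 12.4.1 to: a fall of at least 1 point, or a rectal bleeding sub-score of 0 at week 8. For a patient entering at 1 to 3, reaching 0 is already a fall, so only bleeding-0 entrants are affected, and they must remain at 0.
2. Keep the current rule as a sensitivity analysis. If unblinding has already happened, keep the current rule as primary and report the amended rule as a sensitivity analysis.
3. Report the number and share with baseline bleeding 0 by arm. Randomisation is unstratified (Section 12.3), so the shares can differ by chance.
4. State in Section 12.1 which response definition the 27% and 55% refer to.
5. As separate tidying, confirm whether more than 3 or at least 3 points is intended, and correct the cross-reference in Section 12.4.1. It points to 10.1.2.2 (adverse event reporting); the definition is in 10.1.1.1.

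The broader 0-or-1 wording of Section 13.2.4 is an option for the sponsor, but it also loosens the rule for patients entering with bleeding 1.

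**Cost.** A protocol amendment with IRB approval, because the primary endpoint changes. No new data are needed: full Mayo scores are already planned at day 0 and week 8. The endpoint becomes somewhat easier to meet in all arms, and a bleeding-0 entrant can respond without any improvement in bleeding. Requiring bleeding of at least 1 at entry would also close the gap, but only for patients not yet enrolled.

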12.4.2 Analysis of Secondary Endpoints

- a. Clinical remission at week 8 post-FMT, as defined by Mayo score ≤ 2 without any sub-score >1
- b. Endoscopic response or remission, as defined as a Mayo endoscopic sub-score 0-1 with at least a 1-point reduction from baseline or a Mayo endoscopic sub-score of 0
- c. Safety will be assessed by:
 1. Subject mucosal biopsies, stool and blood testing.
 2. Subject symptomatology via medical interview, physical exam, and Mayo score and change in standard UC medications.
 3. Number and type of treatment related adverse events
 4. Number and type of disease-related complications such as hospitalizations, surgeries and endoscopies, medical complications, and mortality.

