13.1.11 Adverse Event Characteristics and Related Attributions

CTCAE term (AE description) and grade: The descriptions and grading scales found in the revised NCI Common Terminology Criteria for Adverse Events (CTCAE) version 5.0 will be utilized for AE reporting in this study and reported to the primary investigator as frequently as adverse events occur. A copy of the CTCAE version 5.0 can be downloaded from the CTEP web site (<http://ctep.cancer.gov>).

- Attribution of the AE:
 - Definite – The AE *is clearly related* to the study treatment.
 - Probable – The AE *is likely related* to the study treatment.
 - Possible – The AE *may be related* to the study treatment.

- Unlikely – The AE is *doubtfully related* to the study treatment.
- Unrelated – The AE is *clearly NOT related* to the study treatment.

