13.1.12 Recording of Adverse Events

All AEs, regardless of seriousness, severity, or causal relationship to FMT, will be recorded in the subject's medical record and/or subject specific AE log. The AE log will be maintained by the research staff and kept in the subject's research chart.

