13.4.2.2 Assessment of Causality

The physician must assess the relationship of any AE (including SAEs) to FMT, as related or not related, based on clinical judgment and using all available information, and may include consideration of the following factors:

- a. Possible alternative causes of the AE, including the disease under treatment, pre-existing conditions, concomitant use of other drugs, and presence of environmental or genetic factors.
- b. The temporal association between FMT exposure and onset of the AE.
- c. Whether the manifestations of the AE are consistent with known actions or theoretical toxicity of FMT.

The causal relationship between FMT and the AE will be assessed using one of the following categories:

- a. Not Related: An AE is not associated with FMT if:
 - An event that can be determined with certainty to have no relationship to the FMT.
 - Temporal relationship is lacking (i.e. the event did not occur within a reasonable time frame following administration of FMT)

[figure not shown]
- Other causative factors more likely explain the event (i.e. pre-existing condition, other concomitant treatments);
- b. Definitely Related:
 - There is a positive temporal relationship (i.e. the event occurred within a reasonable time frame following FMT)
 - The AE is more likely explained by FMT than by another cause
 - Previously known toxicity of FMT.
- c. Probably Related:
 - There is a positive temporal relationship (i.e. the event occurred within a reasonable time frame following FMT)
 - The AE is more likely explained by FMT than by another cause
 - Unlikely to be explained by patient's clinical state or other intervention.
- d. Possibly Related:
 - There is a positive temporal relationship (i.e. the event occurred within a reasonable time frame following FMT)
 - Event follows an expected response pattern to FMT, but event could have occurred secondary to a number of other factors.

14. Unanticipated Problems Involving Risks to Subjects or Others

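### The only adverse event count in 12.4.2(c) is limited to treatment-related events, with no scale or cut-off named and two attribution schemes that differ; an all-cause comparison by arm to week 8 should be added

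*Combined protocol and SAP*

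**What the plan says.** Section 12.4.2(c) assesses safety by four items:

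- c.1: biopsies, stool and blood tests.
- c.2: "Subject symptomatology via medical interview, physical exam, and Mayo score and change in standard UC medications".
- c.3: "Number and type of treatment related adverse events".
- c.4: "Number and type of disease-related complications such as hospitalizations, surgeries and endoscopies, medical complications, and mortality".

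Item c.3 cites no scale and no cut-off.

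Attribution is described twice. Section 13.1.11 grades each event against the study treatment on five levels, the fourth being an event that is "doubtfully related". Section 13.4.2.2 first asks the physician for a two-way judgement, related to FMT or not, and then says: "The causal relationship between FMT and the AE will be assessed using one of the following categories". Four categories follow, none of them 'unlikely'.

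Recording is not filtered. Section 13.1.12 states: "All AEs, regardless of seriousness, severity, or causal relationship to FMT, will be recorded". Section 13.4.1 repeats that documentation does not depend on relationship. Section 12.1 plans four between-group comparisons for secondary efficacy and safety. Section 15.3 promises the percentages of patients with any adverse event and any serious one, for the FDA annual report, without saying by arm.

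**The concern.** In a randomised comparison the control arm already shows how many events would have occurred without the treatment. A count restricted to events that a physician calls related adds a subjective step. Here that step is not tied to either scheme, and the two schemes refer to different treatments. The same event can then enter or leave c.3 according to which section the physician followed.

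This matters most for psyllium. Section 15 says that the trial should inform on the safety of fiber supplements as well as FMT, yet one of the two schemes does not ask about psyllium at all. An event judged neither treatment-related nor disease-related falls outside both c.3 and c.4, although it has been recorded.

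**Working it through.** **1. The plan's own figure.** The only design figure is for efficacy (12.1): 55% v 27%, 45 per arm, two-sided 0.05, about 80% power. With unpooled variance, n = (1.960 + 0.842)² × (0.55×0.45 + 0.27×0.73) / 0.28² = 7.849 × 0.4446 / 0.0784 = 44.5, so 45. It reproduces; the pooled formula gives 78.0% power at 45. There is no safety figure to reproduce, and nothing below changes this one.

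**2. The two schemes side by side.**

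| | 13.1.11 | 13.4.2.2 |
|---|---|---|
| Reference | study treatment | FMT |
| Levels | definite, probable, possible, unlikely, unrelated | related / not related; then definitely, probably, possibly, not related |
| Cut-off for 'related' | none | the two-way question, not mapped to the four levels |
| Psyllium | covered, if it counts as study treatment (it is a study intervention in Section 7) | not covered |

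**3. A psyllium event.** Section 13.1.7 names choking and bloating as psyllium risks. Under 13.1.11, bloating ascribed to psyllium can be definite, probable or possible. Under 13.4.2.2 the question is whether FMT caused it, and a more likely cause among other concomitant treatments is a ground for 'not related'. The event can count under one scheme and not under the other.

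**4. Size, with assumed rates.** The documents give no event rates or attribution shares. Let c be the background rate, e the true excess, and s and t the shares of background and excess events called related.

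- *No true effect, unequal attribution.* With s = 50% in one group and 30% in the other, the false difference is c × (0.50 − 0.30): 4, 8 and 12 points for c = 20%, 40% and 60%. The all-event difference is 0.
- *True excess of 10 points, half called related.* The related-only difference is 0.5 × 10 = 5 points.
- *Power, 90 FMT v 45 placebo.* Power = Φ[(d − 1.96·SE0)/SE1], where SE0 = √(p̄(1−p̄)(1/45 + 1/90)) and SE1 = √(p0(1−p0)/45 + p1(1−p1)/90).

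| Count | Placebo v FMT | SE0, SE1 | Power |
|---|---|---|---|
| All events, c = 20%, e = 20 points | 20% v 40% | 0.0861, 0.0789 | Φ(0.397) = 65% |
| Related, s = t = 50% | 10% v 20% | 0.0680, 0.0615 | Φ(−0.543) = 29% |
| Related, s = 20%, t = 90% | 4% v 22% | 0.0669, 0.0525 | Φ(0.929) = 82% |

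At c = 40% and e = 20 points, all events give 59.5% and related events with s = 20%, t = 90% give 72.6%. The direction depends on how accurate attribution is.

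- *Precision.* At 40% in both groups the 95% half-width is 1.96 × √(0.24 × (1/90 + 1/45)) = 17.5 points for 90 v 45, and 1.96 × √(0.24 × 2/45) = 20.2 points for 45 v 45.

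**5. What limits an all-event comparison.**

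- The placebo group receives active FMT at week 8 (6.1.2.2, 7.8.1), so later events no longer compare FMT with placebo.
- Section 13.2.4 takes recurrent UC flares out of adverse event reporting.
- Section 13.4.1 starts monitoring after FMT in one place and recording after consent in another. Section 12.6.1 starts toxicity at the first FMP250 treatment. Psyllium starts on day −3 (6.1.1), so events in those days may or may not be captured.

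**The case against.** The strongest reply is that c.3 is one of four items. Items c.1 and c.2 carry no attribution filter, and c.4 is conditioned on the disease rather than the treatment. Between-group safety comparisons are already planned, and any-event percentages go into the annual report. All of that stands. A reader might infer that the safety assessment as a whole counts only related events; the documents do not support that. What remains is that c.3 is the only adverse event count and that no all-cause comparison by arm is named.

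Four other stronger readings also fail:

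- *The definitions of 'definite' and 'probable' distort the count.* Both list "The AE is more likely explained by FMT than by another cause", and only the first requires a known toxicity. That is untidy, but both levels are related under any plausible cut-off, so c.3 does not change.
- *Restricting to related events loses power.* This holds if attribution is no better than chance and reverses if it is accurate (65% v 29% in one case, 65% v 82% in the other). The plan makes no power claim for safety.
- *Attribution is biased.* Sections 3.1 and 6.1.1 describe clinicians and assignment as blinded. Where FMT blinding holds, misattribution should be similar in the FMT and placebo groups. For psyllium no placebo powder is described, so knowledge of assignment is plausible, but bias is a risk and is not shown.
- *An all-event comparison would be unbiased.* It would not be after week 8. For the fiber contrast, knowledge of assignment can affect which events are reported at all, and dropping attribution does not cure that.

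**Conclusion.** The point holds as a cheap improvement to a secondary, unpowered endpoint. Item c.3 has no scale and no cut-off. The two schemes differ in levels and in reference treatment, and the mismatch can move psyllium events in or out of the count. The events needed for an all-cause comparison by arm are already recorded, apart from flares and possibly events before FMT.

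No size can be taken from the documents. The 4 to 12 point false excess rests on assumed background rates of 20% to 60% and assumed attribution of 50% v 30%. It lies within the sampling error of a comparison this small (half-width 17.5 to 20.2 points at a 40% rate). The claim that a psyllium event could be classified both ways assumes that the study treatment in 13.1.11 includes psyllium.

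**What to change.** 1. Reword 12.4.2 c.3 as the number and percentage of subjects with any adverse event and with any serious adverse event, by type, compared between randomised arms up to the week 8 procedure.
2. State one start point. Reconcile the two statements in 13.4.1 with each other and with 12.6.1, given that psyllium starts on day −3.
3. Report events after the week 8 procedure separately, because the placebo group then receives active FMT.
4. Tabulate UC flares by arm, because 13.2.4 keeps them out of adverse event reporting.
5. Keep related events as a supportive analysis on one scale, with a stated cut-off, covering both FMT and psyllium. Align 13.1.11 and 13.4.2.2 to it.
6. State that the fiber contrast remains open to reporting bias, since no placebo powder is described.

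The cost is protocol and SAP wording and a few more tables. No new collection is needed for events already recorded; settling the start point may add the days before FMT. Sample size, alpha and power do not change. The all-event comparison may have less power than a related-only count if attribution is accurate, which is why the related count is kept.
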